**11. Please check which quit aid(s) you are currently using:**

Nicotine gum  
 Nicotine lozenge  
 Nicotine patch  
 Nicotine nasal spray  
 Nicotine inhaler  
 Chantix® (Varenicline)  
 Zyban® or Wellbutrin® (Bupropion)  
 Other (please specify): \_\_\_\_\_

**12. Do you ever forget to use your medicine / NRT?**

YES  
 NO

**13. Are you sometimes careless about using your medicine / NRT?**

YES  
 NO

**14. Sometimes when you feel worse about your medicine / NRT, do you stop using it?**

YES  
 NO

**15. When you feel better do you sometimes stop using your medicine / NRT?**

YES  
 NO

**16. How helpful was the app with staying adherent to your cessation medication or NRT?**

*Not at all*    *A Little*    *Somewhat*    *Very*    *Extremely*

**17. Please answer the user experience / satisfaction questions to the best of your ability.**

|   | Not at all | A Little | Somewhat | Very | Extremely |
|---|-------------------|-----------------|-----------------|-------------|------------------|
| How satisfied were you with the app experience?       | 1                 | 3               | 4               | 6           | 7                |
| How easy was the app to use for your quit attempt?    | 1                 | 3               | 4               | 6           | 7                |
| How helpful was the app as part of your quit attempt? | 1                 | 3               | 4               | 6           | 7                |

**18. Please answer these smoking-related questions to the best of your ability**

|  | Not at all | Very Little | A Little | Moderately | A lot | Quite a lot | Extremely |
|--|-------------------|--------------------|-----------------|-------------------|--------------|--------------------|------------------|
| Do you find cigarettes satisfying?     | 1                 | 2                  | 3               | 4                 | 5            | 6                  | 7                |
| Do cigarettes taste good to you?       | 1                 | 2                  | 3               | 4                 | 5            | 6                  | 7                |
| Do you enjoy smoking cigarettes?       | 1                 | 2                  | 3               | 4                 | 5            | 6                  | 7                |
|  | Not at all | Very Little | A Little | Moderately | A lot | Quite a lot | Extremely |
| Does smoking cigarettes calm you down? | 1                 | 2                  | 3               | 4                 | 5            | 6                  | 7                |

|   |   |   |   |   |   |   |   |
|---|---|---|---|---|---|---|---|
| Does smoking cigarettes make you feel more awake?     | 1 | 2 | 3 | 4 | 5 | 6 | 7 |
| Does smoking cigarettes make you feel more irritable? | 1 | 2 | 3 | 4 | 5 | 6 | 7 |
| Does smoking cigarettes help you concentrate?         | 1 | 2 | 3 | 4 | 5 | 6 | 7 |
| Does smoking cigarettes reduce your hunger for food?  | 1 | 2 | 3 | 4 | 5 | 6 | 7 |

|  | Not at all | Very Little | A Little | Moderately | A lot | Quite a lot | Extremely |
|--|------------|-------------|----------|------------|-------|-------------|-----------|
| Does smoking cigarettes make you less dizzy? | 1          | 2           | 3        | 4          | 5     | 6           | 7         |
| Does smoking cigarettes make you nauseous?   | 1          | 2           | 3        | 4          | 5     | 6           | 7         |

|  | Not at all | Very Little | A Little | Moderately | A lot | Quite a lot | Extremely |
|--|------------|-------------|----------|------------|-------|-------------|-----------|
| Do you enjoy the sensation in your throat and chest when you smoke cigarettes? | 1          | 2           | 3        | 4          | 5     | 6           | 7         |
|  | Not at all | Very Little | A Little | Moderately | A lot | Quite a lot | Extremely |
| Does smoking cigarettes immediately relieve your craving for a cigarette?      | 1          | 2           | 3        | 4          | 5     | 6           | 7         |

**19. How much of the time have you felt the urge to smoke in the past week? (Circle one number)**

| Not at all | A little of the time | Some of the time | A lot of the time | Almost all the time | All of the time |
|------------|----------------------|------------------|-------------------|---------------------|-----------------|
| 0          | 1                    | 2                | 3                 | 4                   | 5               |

**20. How strong have the urges been? (Circle one number)**

| No urges | Slight | Moderate | Strong | Very Strong | Extremely Strong |
|----------|--------|----------|--------|-------------|------------------|
| 0        | 1      | 2        | 3      | 4           | 5                |

**21. Please show for each of the items below how you have been feeling over the past week?**

|                     | Not at all | Very Little | A Little | Moderately | A lot | Quite a lot | Extremely |
|---------------------|------------|-------------|----------|------------|-------|-------------|-----------|
| Depressed           | 1          | 2           | 3        | 4          | 5     | 6           | 7         |
| Anxious             | 1          | 2           | 3        | 4          | 5     | 6           | 7         |
| Irritable           | 1          | 2           | 3        | 4          | 5     | 6           | 7         |
| Restless            | 1          | 2           | 3        | 4          | 5     | 6           | 7         |
| Hungry              | 1          | 2           | 3        | 4          | 5     | 6           | 7         |
| Poor Concentration  | 1          | 2           | 3        | 4          | 5     | 6           | 7         |
| Poor Sleep at Night | 1          | 2           | 3        | 4          | 5     | 6           | 7         |

**22. Have you experienced any of the following over the past week? (Circle one number for each item)**

|                     | No | Slight | Moderate | Severe | Very Severe |
|---------------------|----|--------|----------|--------|-------------|
| Sores in the mouth  | 1  | 2      | 3        | 4      | 5           |
| Constipation        | 1  | 2      | 3        | 4      | 5           |
| Cough / Sore Throat | 1  | 2      | 3        | 4      | 5           |

**23. At any point during the study did you experience a negative health event?**

- No
- Yes - please describe the negative health event you experienced:

*[The following questions will only be presented to user if answers "Yes" to the previous question]*

**What negative health event did you experience? \_\_\_\_\_**

**When did the negative health event occur mm/dd/yyyy**

**If you experienced a negative health event, did it impact your ability to carry out your typical daily functions?**

- No
- Yes - please describe how your daily life was affected by the negative health event:

**If you experienced a negative health event, did you seek any professional care to address the negative health event you experienced?**

- No
- Yes - please describe the professional care you received:

**What was the outcome of this negative health event?**

- resolved completely
- partially resolved
- ongoing

**During the study did you experience any other negative health event?**

- No
- Yes

[A portion of the study populations that completes the outcome survey will be invited to conduct the CO assessment via livevideo monitoring to confirm identity. Participants that are invited to conduct the CO assessment via live video monitoring will consent to participate in live video monitoring at the end of the outcome survey by answering “Yes” or “No”. Study participants that answer “Yes” will then select their preference of video platform and will then be linked to schedule a video call via Calendly with the research coordinator. Those who do not consent to participate in the live video monitoring CO assessment will receive a reminder to submit the end of study CO assessment.]

**24. Would you like to participate in completing the CO assessment via live video-monitoring- you'll receive an additional \$50 Amazon gift certificate?? (you will need another device: computer or phone with video capabilities in order to submit the assessment)**

- If NO, remote CO assessment reminder
- If YES, Video monitoring preference, link to Calendly schedule

You have reached the end of the survey. Please click “Finish” to submit your survey responses

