#### **7.4 Study Completion**

Study termination letters will be emailed or mailed to participants upon loss to follow up or upon study completion (completion of the Outcome Survey).

Additionally, all participants that were randomized into the clinical trial will be emailed or mailed documentation revealing the study sponsor as “Click Therapeutics” along with a brief explanation of the sponsor’s masking rationale. (See Appendix **15.14**).

There will be no long-term follow-up of users after the 8-week outcome survey is completed.

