permanently or substantially disabling event, event requiring or prolonging inpatient hospitalization, or any congenital anomaly. This also includes any event that a study investigator judges to impose a significant hazard, contraindication, side effect, or precaution. For purposes of this study, all SAEs will be required to be reported to the IRB and NIDA, regardless of any judgment of their relatedness to the study intervention. All relevant information will be reported including information about the event and its outcome, the subject's medical history and current conditions, and any relevant laboratory data. Information will be reviewed and a determination made of whether there was any possible relevance to the study intervention. Reporting to Western IRB and NIDA will be done within 72 hours of detection of the SAE.

Non-Serious Adverse Events: In monthly data review meetings, the PI will review summaries of the numbers and rates of adverse events by treatment group compiled by the research coordinator. These reports will include types of events, severity, and outcome if available. At the same intervals, the PI will also receive summary reports of treatment retention and reasons for drop-out, by treatment arm. In the event that differences in AE or retention rates between groups are apparent, the PI will consult with NIDA to determine further evaluation of safety.

Study Stopping Rules: If at any time during the course of the study, the PI or NIDA judges that risk to subjects outweighs the potential benefits, either shall have the discretion and responsibility to recommend that the study be terminated.

Monitoring of Data Quality: In the monthly Data and Safety monitoring meeting the PI will receive a report on data quality and completeness. At a minimum, this will include an overview of the progress of patient intake and retention; summary reports describing patient compliance with surveys and CO monitoring as described in the protocol; and a summary of the completeness and quality of key data elements needed to characterize patients and their primary and secondary outcomes.

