## **CONFIDENTIAL**

If an adverse event is reported and evaluated by the study physician and is deemed to be severe enough to require withdrawal from the study, the participant will be withdrawn. Participants will have access to the e-mail and phone number of a study coordinator in case they are experiencing discomfort with Clickotine®.

All Adverse Events that occur during study participation will be solicited from study participants in both groups via an email-based system for reporting AE/SAEs. Participants are made aware of the email system during the informed consent and study enrollment process. Reports are reviewed by the research coordinator and the PI within 24 hours of the report and conveyed to the Medical Monitor (MM) for review and follow-up if appropriate. A Medical Monitoring form (See Appendix 12.6) is completed for each AE reported to the MM, to include: a description of the event; onset/offset dates; treatment required and/or condition resolution; designation as AE/SAE; and judgment of association with study intervention.

Expedited review will occur for all events reported by study participants that meet the FDA definition of Serious Adverse Events (SAEs) – i.e., any fatal event, immediately life- threatening event, permanently or substantially disabling event, event requiring or prolonging inpatient hospitalization, or any congenital anomaly. This also includes any event that a study investigator judges to impose a significant hazard, contraindication, side effect, or precaution. Reporting to NIH will be done according to NIH regulations governing SAE reporting: the PI will contact NIDA within 72 hours after the detection of a SAE. Reporting of Suspected Unexpected Serious Adverse Reactions (defined by WIRB as "unanticipated adverse device effects") to Western IRB will be done within 5 days of the report in accordance with WIRB policy.

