**Participant ID:**

**Description of the event:**

**Onset date:**

**Offset date:**

**Treatment required:**

**Resolution (select one):**

**Resolved completely**

**Partially resolved**

**Ongoing**

**Medical Monitor Designation (select one from each section):**

**Adverse Event**

**Serious Adverse Event**

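### The Outcome Survey takes details of only one negative health event per participant and has no stated route to the Medical Monitoring form, and no severity field or scale supports the promised monthly severity summary

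*Protocol*

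**What the plan says.** **Survey.** Question 23 in Protocol 15.4 asks "At any point during the study did you experience a negative health event". A Yes opens one set of follow-up items: what the event was, when it occurred, its effect on daily life ("did it impact your ability to carry out your typical daily functions"), any professional care sought, and "What was the outcome of this negative health event" (resolved completely, partially resolved or ongoing). The block closes with "During the study did you experience any other negative health event", answered No or Yes. The next printed text is the invitation to video-monitored CO testing.

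**Form.** Protocol 9.3, repeated in the SAP's Data and Safety Monitoring Plan, solicits AEs in both arms by email and requires a Medical Monitoring form for each AE that reaches the Medical Monitor. The form is to contain "a description of the event; onset/offset dates; treatment required and/or condition resolution; designation as AE/SAE; and judgment of association with study intervention". The form itself (Protocol Section 16) asks for participant ID, description, onset date, offset date, treatment required and resolution. Then, under "Medical Monitor Designation (select one from each section", it offers AE, SAE, suspected unexpected serious adverse reaction or none of these, and related or not related. Its heading says that it is completed when a participant reports an event through the email system.

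**Monthly review.** Protocol 9.2 and the DSM Plan Administration part of the SAP have the PI review numbers and rates of non-serious AEs by treatment group: "These reports will include types of events, severity, and outcome if available".

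**The concern.** There are two separate gaps between what is to be reported and what is recorded.

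First, the survey followed as written turns a participant's second event into a bare Yes. Nothing on record then allows it to be counted by type, dated, called serious or judged related. A participant with several events is one whom safety monitoring should not lose, and the event left without details could be the more important one. In addition, no text sends even the first survey-reported event to the Medical Monitor.

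Second, severity is promised in the by-arm summaries, but no form field holds it and no scale defines it. Whoever compiles the summary would have to infer severity from free text, by a rule not fixed in advance. Under Protocol 5.4 and 9.2 the compiler is the research coordinator, who is also the one team member who knows the assignments.

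**Working it through.** The plan states no figure on this point, so there is none to reproduce. The check compares the instruments with the promise and then estimates scale.

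**1. Is a repeat block written?** 15.4 writes out its branching elsewhere: a Yes to any of questions 1–3 opens the Fagerström items, a Yes to question 10 opens questions 11–16, and a Yes to question 23 opens the detail items. After the further-event question there is no loop, free-text field or follow-up contact. Whether the live survey looped cannot be known from the text.

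**2. Does a survey event reach the form?** The Section 16 heading names only email reports. Protocol 9.3 describes only the email route. In the pilot, by contrast, all reported events went to the medical monitor, who could obtain more information through the study team (SAP, Trial Safety). Neither step is restated for this trial.

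**3. Which channel yields events?** Pilot (SAP, Trial Safety): 4 spontaneous + 32 from the focused survey question = 36, and 32/36 = 89% from the survey. The pilot's spontaneous channel was in-app and this trial's is email, so 89% is a guide and not an estimate for this trial.

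**4. Is severity recorded anywhere else?** The AE/SAE designation records seriousness, which is a different attribute. Survey question 22 grades mouth sores, constipation and cough or sore throat, and question 21 rates mood, sleep and similar symptoms. Both cover the past week only and do not grade reported events. The content list in 9.3, its two repeats in the SAP and the form all lack a severity entry.

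**5. Expected scale.** Inputs: 156 participants (Protocol 4.1), 416 enrolled and 365 completers in the pilot (Protocol 1.3), and the pilot event counts above (19 of the 36 were judged clinically significant). With rate r per participant and events Poisson at a common rate (an assumption, since the documents give no events per person):

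- expected events = 156 × r
- P(two or more) = 1 − e^(−r)(1 + r)
- expected participants with two or more = 156 × P(two or more)
- chance of at least one such participant = 1 − (1 − P(two or more))^156

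| Basis | r | Events | Participants with ≥2 | Chance of at least one |
|---|---|---|---|---|
| Survey events, 32/416 | 0.0769 | 12.0 | 0.44 | 0.36 |
| All events over completers, 36/365 (high) | 0.0986 | 15.4 | 0.71 | 0.51 |
| Clinically significant only, 19/416 (low) | 0.0457 | 7.1 | 0.16 | 0.15 |

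The first row allows for non-response, because 32/416 counts events per person enrolled. Using 32/365 on 156 × 365/416 = 136.9 completers gives the same 12.0 events and 0.50 participants with two or more.

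The severity gap does not depend on these counts. It applies to every form completed.

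**The case against.** The strongest reply is that the survey is not the only channel. Email solicitation runs throughout participation, has no one-event limit, is reviewed within 24 hours and provides for follow-up by the Medical Monitor where appropriate. Participants also have the coordinator's email address and telephone number. The survey's event field is free text, so a participant could name two events in it. All of this stands, and it limits the first gap to further events disclosed only in the survey and not followed up. A reader might infer that later events can never be classified, but the documents do not support that.

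On severity, the description, treatment required, effect on daily function, care sought and AE/SAE designation would let someone judge severity afterwards. The phrase *if available* may also qualify the whole list and not just outcome. So the summary is not impossible to produce. What is missing is a defined and recorded basis for it.

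Three further inferences are tempting and fail:

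- *Severity differences between arms trigger consultation with NIDA.* The trigger in the non-serious AE paragraph is differences in AE or retention rates. The general safety trigger in 9.2 does not name severity either.
- *Withdrawal rests on unrecorded data.* Protocol 9.3 rests it on the study physician's evaluation of a reported event, which needs no form field.
- *Unresolved events need an exception to 7.4.* The form accepts Ongoing and Partially resolved, so an open offset date is a valid entry. The sentence "There will be no long-term follow-up of users after the 8-week outcome survey is completed" does not bar a clarifying contact about an AE.

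**Conclusion.** The point holds in limited form, as a safety-data completeness matter that does not touch the primary efficacy analysis.

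As written, the survey holds details of one event per participant, and survey-reported events have no stated route to the Medical Monitoring form. Further events known only from the survey cannot be designated. The likely loss is detail for 0 to 1 participants (expected 0.2 to 0.7). This assumes that pilot rates carry over and that events are Poisson at a common rate. Clustering within people would raise it. A reader might instead suppose that 10–30% of those reporting have a second event, which would give 12 × 0.10 = 1.2 to 12 × 0.30 = 3.6 events. No document gives such a share, and the pilot's 32 counts events and not people, so it may already include second events.

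The severity gap is certain on the printed forms and covers every AE. A severity summary is promised by arm, with no field or scale behind it. The repair is small enough to be worth making even though the expected count is low.

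**What to change.** 1. In Protocol 15.4, if the further-event question is answered Yes, repeat the detail items (event, date, daily function, care sought, outcome) until the answer is No.
2. Add a severity grade with a stated definition to the Medical Monitoring form in Section 16, and add it to the list of form contents in Protocol 9.3 and its two repeats in the SAP.
3. Extend the form's trigger in Section 16 to events reported in the Outcome Survey, and say in 9.3 that these go to the Medical Monitor.

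Cost: one skip-logic change, one form field and a sentence or two of text. The survey becomes slightly longer for the few participants with several events, and the Medical Monitor completes a few more forms (about 12 survey-reported events are expected in total). Treatment, eligibility, sample size and the efficacy analysis do not change.

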## 15.5 My Digital Study Welcome Card

Welcome to the Digital Smoking Cessation study!

Congratulations on beginning your journey to a smoke free life!

As part of the study, and to show our gratitude, you are receiving a Smokerlyzer.

Please test it at your earliest convenience and submit the CO value to ensure it works properly. We highly encourage you to use it throughout the study to track your progress and motivate you. Not only will regularly using your Smokerlyzer push you to keep seeing your CO values drop, it will also ensure that your Smokerlyzer is working properly.

While not required, we would really appreciate it if you submitted your values throughout the study. Doing so allows us to better support you throughout your journey.

As you prepare to begin this new experience, remember to stay strong and that you’re not alone. We’re here with you every step of the way!

Sincerely,  
My Digital Study Team

### To get started:

1. Download the Smokerlyzer app on the AppStore or Google play store
2. Enter the pin code on your Smokerlyzer and the prompted information into the app

### Smokerlyzer instructions for use:

1. Plug the white cord into the Smokerlyzer and into your phone’s headphone jack
2. Take a deep breath and hold it for 15 seconds
3. Exhale into the Smokerlyzer
4. Readings will appear on your phone instantly
5. Results will be explained and charted

Go to this [\[LINK\]](#) for the iCO Smokerlyzer device video instructions ☺

